## 8.3.2. Primary Estimand

The primary estimand, the main clinical quantity of interest to be estimated in the study, is defined by the following three components:

- Population: patients with treatment-resistant depression with the DGM4-positive biomarker
- Endpoint: change in MADRS total score from baseline to Day 42
- Measure of Intervention: the effect of the initially randomized treatment that would have been observed had all patients remained on their treatment throughout the double-blind phase

The primary analysis will be based on the full analysis set, as described above, and the MADRS total scores collected during the double-blind treatment period.

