5.4.1.1. Estimand

The following components are considered in the construction of the estimand, the main clinical quantity of interest to be estimated in the study:

- Objective: To demonstrate that liafensine (1 mg QD or 2 mg QD) is superior to placebo in DGM4-positive patients with TRD as assessed by the change in MADRS total score from baseline to Day 42 of double-blind treatment
- Intercurrent events (ICEs): Early termination of treatment due to various reasons or starting a prohibited medication. A detailed list of ICEs is provided at the end of this section.
- Question of interest: For a patient with TRD for whom a short-term monotherapy would be indicated, what would be the expected effect of liafensine on severity of depressive

episodes at Week 6, if taken as directed for 6 weeks without initiating prohibited medications as defined in Protocol Section 5.3?

The primary estimand is defined with the following components per ICH E9(R1):

- The treatment condition of interest: TRD patients who meet all eligibility criteria will be randomized in a 1:1:1 ratio to receive either placebo QD, liafensine 1 mg QD, or liafensine 2 mg QD for 6 weeks.
- Population: patients with TRD with the DGM4-positive biomarker
- Endpoint at subject level: change in MADRS total score from baseline (Visit 3, Day -1) to Day 42 (Visit 7)
- Population-level summary: For each treatment arm, the least-square (LS) mean of the primary endpoint will be calculated in each arm using the method described in Section 5.4.1.2. Treatment comparisons will be based on the LS means.

Intercurrent events and corresponding strategies:

Intercurrent events to be considered for this analysis are those events that cause the MADRS at Day 42 to be either missing or compromised. The primary method will be mixed model for repeated measures (MMRM) with imputation assuming missing at random (MAR), ie, a hypothetical strategy per ICH E9(R1). Hence, missing values will be imputed with non-missing values in the same treatment group. A fully conditional specification (FCS) method with predictive mean matching approach will be used in the imputation of missing MADRS score change from baseline as continuous variables (Buuren 2007). The following sensitivity analyses will be performed, with details described in Section 5.4.1.3:

- A tipping-point analysis for the primary analysis result
- MMRM without imputation

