In the analysis, data collected after initiation of prohibited medications will be used unless otherwise specified. All available data collected from all subjects before or after ICEs will be included in the analysis unless otherwise specified. Missing data due to any ICEs will be imputed using SAS MI procedure with the FCS statement and REGPMM option to implement the fully conditional specification method with predictive mean matching approach described in Section 5.4.1.1. For MADRS, the total score is set to missing if 50% or more items are missing at an assessment. When this occurs, the change from baseline value will be imputed without using any of the non-missing items.

The following variables will be included in the imputation model: region, baseline MADRS score, and change from baseline at Weeks 1, 2, 4, and 6. One hundred fully imputed datasets will be created. The MMRM described above will be used for treatment comparisons. Treatment effects (difference in LS means between treatment arms) from these 100 analyses will be combined to generate final results using Rubin's method implemented by SAS MIANALYZE procedure.

The following tables and figures will be generated to assess the MAR assumption:

- 1. A by-visit and overall summary table for (n, %), and cumulative (n, %) for reasons of missing value or early dropout in each arm due to:
 - AE including death
 - Withdrawal of consent to treatment discontinuation
 - Other reasons
 - Total (All of the above)

Within each arm, the summary statistics of the primary endpoint will also be generated by dropout reason at each visit. This table will also be used to support the figure below.

- 2. For each arm, generate a line graph for mean change from baseline (y-axis) over time (x-axis) by dropout reasons. There will be 4 lines on this figure to represent each dropout reasons:
 - None (completers)
 - Dropout due to AE including death
 - Dropout due to withdrawal of consent to treatment discontinuation
 - Dropout due to other reasons

In addition, a figure similar to the one above will be generated, with mean change from baseline replaced with a line graph for each subject. Subjects with the same reason for dropout will have the same color.

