The same model in the primary analysis will be used without imputation using the treatment policy strategy per ICH E9(R1) (Polverejan 2023). This analysis will be used to assess the impact of imputing missing values based on the MAR assumption.

3. MMRM with imputation using pattern mixture model

This sensitivity estimator will be using a control-based multiple imputation method (Ratitch 2013). This sensitivity analysis does not rely on the MAR assumption. Data collected after initiation of prohibited medications will not be used unless otherwise specified. Missing data due to all ICEs will be handled per specifications below unless otherwise specified.

In this sensitivity analysis, imputation will be implemented using SAS MI procedure with FCS statement and REGPMM option, as well as MNAR statement with MODELOBS option to identify observations from the placebo arm for deriving the imputation models, ie, assuming all missing data will have a profile that equals the profile of the placebo arm for all time points. The variables to be used in the imputation are region, baseline values, and change from baseline values observed at Weeks 1, 2, 4, and 6.

One hundred fully imputed datasets will be created. The MMRM described in Section 5.4.1.2 will be used for treatment comparisons. Treatment effects (difference in LS means between treatment arms) from these 100 analyses will be combined to generate the final results using Rubin's method with SAS MIANALYZE procedure.

A tipping point analysis for this sensitivity analysis will also be conducted to assess the robustness of the result. The same steps described in the first sensitivity analysis will be followed.

4. Sensitivity Analyses based on RAS

A set of sensitivity analyses listed below will be performed using DGM4-positive patients in RAS. The same MMRM in the primary and sensitivity analyses described above will be carried out with the exclusion of the following fixed effect: treatment by baseline MADRS total score. In other words, the model will include the fixed effects of treatment, visit (categorical covariate), treatment by visit interaction, baseline MADRS total score (continuous covariate), and region.

The following analyses will be performed in this set of sensitivity analyses:

- 1) The primary analysis, as well as the 1st and 2nd sensitivity analyses based on FAS will be repeated using RAS.

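### The stated primary estimand is hypothetical, but the main estimator keeps MADRS values observed after intercurrent events, and no planned FAS analysis with the primary model estimates the stated quantity

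*SAP*

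**What the plan says.** **Target.** Protocol 8.3.2 defines the measure of intervention as "the effect of the initially randomized treatment that would have been observed had all patients remained on their treatment throughout the double-blind phase". The question of interest in SAP 5.4.1.1 is the effect of liafensine at Week 6 "if taken as directed for 6 weeks without initiating prohibited medications as defined in Protocol Section 5.3". Both are hypothetical targets. SAP 5.4.1.1 counts as intercurrent events those that leave Day 42 MADRS missing or compromised, and its list includes prohibited medication, several kinds of treatment discontinuation, and death.

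**Label.** SAP 5.4.1.1 describes the primary method as MMRM "with imputation assuming missing at random (MAR), ie, a hypothetical strategy per ICH E9(R1".

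**Data used.** SAP 5.4.1.2 states: "In the analysis, data collected after initiation of prohibited medications will be used unless otherwise specified". It continues: "All available data collected from all subjects before or after ICEs will be included in the analysis unless otherwise specified". Nothing else in that section overrides this, and the sample code in SAP 8.1 selects records by visit, DGM4 status and group, with no filter for intercurrent events.

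**Neighbouring analyses.** Sensitivity 2 in SAP 5.4.1.3 is introduced with: "The same model in the primary analysis will be used without imputation using the treatment policy strategy per ICH E9(R1". Sensitivity 4, part 1, reads: "The primary analysis, as well as the 1st and 2nd sensitivity analyses based on FAS will be repeated using RAS". Part 2 applies its own imputation rule to each group of events. SAP Table 4 lists the move to multiple imputation but not the handling of post-event data.

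**The concern.** Imputing missing values under MAR addresses only the missing part of the SAP's own definition. Compromised values, such as a Day 42 rating taken on a prohibited antidepressant, enter the primary estimate as observed. SAP 5.4.1.3 itself says that prohibited medication may plausibly add efficacy and removes the affected data for that reason, but not in the analysis that carries the hypothetical label.

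At stake is what the reported number means. The study report would present the primary estimate as the effect under full adherence and no prohibited medication, when it mixes that with the effect regardless of those events. A reader who wanted the stated quantity could not find it in another FAS analysis with the same model.

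**Working it through.** **1. Does any planned analysis estimate the stated target?** It would have to remove values after prohibited medication and after stopping study drug, then impute from the same arm.

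| Analysis (SAP 5.4, 5.4.1.2, 5.4.1.3) | Set, model | Values after prohibited medication | Values observed off drug, no prohibited medication | Source for missing values |
|---|---|---|---|---|
| Primary | FAS, primary | kept | kept | same arm |
| Tipping point | FAS, primary | kept | kept | same arm, then shifted |
| Sensitivity 2 | FAS, primary | kept | kept | none (likelihood) |
| Sensitivity 3 | FAS, primary | removed | kept | placebo |
| Sensitivity 4, part 1 | RAS, no treatment-by-baseline term | kept | kept | as in the analysis repeated |
| Sensitivity 4, part 2 | RAS, no treatment-by-baseline term | removed, same arm | kept | by reason |
| Per protocol | whole patients dropped | kept in those who remain | kept in those who remain | same arm |

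No row meets the requirement. No FAS or RAS row removes off-drug values when no prohibited drug was started: sensitivity 4, part 2, groups only early discontinuers with missing data. The per-protocol set drops whole patients, for disallowed medication only above 50% of the treatment period.

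**2. Does sensitivity 4, part 1 against part 2, isolate prohibited medication?** It holds analysis set and model fixed, but three other things change: missing data after AE discontinuation are imputed from placebo; the one death has its own rule, a normal draw centred on that patient's worst score; and in SAP 8.5 the same-arm imputation model for the liafensine arms is built on completers, whereas SAP 8.1 uses all patients in the arm.

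The AE change alone can matter. Assume SDs of 6, 7, 8 and 9 at Weeks 1, 2, 4 and 6, correlation 0.7 between adjacent visits (AR(1)), and 25, 50, 75 and 100% of a 4.5-point benefit at those visits. For a last rating at Week 1, the placebo-model and same-arm-model means at Week 6 differ by 4.5 − (0.7³ × 9/6) × 1.125 = 3.92 points. For Weeks 2 and 4 the gaps are 3.08 and 1.84. If 5 to 10% of liafensine patients are AE dropouts, the estimate falls by 0.05 × 1.84 = 0.09 to 0.10 × 3.92 = 0.39 points, the same order as the prohibited-medication shift in step 4.

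**3. The plan's own sample size.** Inputs from SAP 2.3: difference 4.5, SD 9, 2-sided 0.05, 80% power, pooled active to placebo 2:1. Placebo n = (1.960 + 0.842)² × 9² × 1.5 / 4.5² = 47.1, against 47 stated. With 94 vs 47, SE = 9 × √(1/94 + 1/47) = 1.608. Power by noncentral t is 79.4% at 2-sided 0.05 and 87.3% at the SAP's 1-sided 0.05. The sample size is not in dispute.

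**4. Illustrative shifts from a true difference of 4.5.** All rates and drug effects here are assumed.

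- Prohibited medication: shift = (use on liafensine − use on placebo) × points gained. With 5 to 10 percentage points difference in use and 4 to 5 points gained: 0.05 × 4 = 0.20 to 0.10 × 5 = 0.50. More use on placebo gives 4.30 to 4.00; more on liafensine gives 4.70 to 5.00; equal use gives no shift.
- Off-drug values: shift = −(share of liafensine patients with a kept off-drug Day 42 value) × effect lost. With 5 to 10% losing half to all of the effect: 0.05 × 2.25 = 0.11 to 0.10 × 4.5 = 0.45, giving 4.39 to 4.05.
- Both worst cases: 0.50 + 0.45 = 0.95, giving 3.55.

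| Estimate targeted | Shift in SE | Power, 1-sided 0.05 |
|---|---|---|
| 5.00 | 0.50/1.608 = 0.31 | 93% |
| 4.50 | 0 | 87% |
| 4.00 | 0.31 | 80% |
| 3.55 | 0.95/1.608 = 0.59 | 71% |

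**5. How many off-drug Day 42 values can there be?** Probably few. Protocol Table 1, footnote f, puts the early-termination rating within 3 days of last dose. At the 44 to 74 hour half-life in Protocol 1.2.3, that is at most 72/74 = 0.97 to 72/44 = 1.64 half-lives. Visit 7 covers Days 35 to 49 (SAP 3.4), so a rating before Day 35 is not a Day 42 value, and MADRS is not scheduled at follow-up. A clearly off-drug Day 42 value needs a patient who stops drug and keeps attending, which Protocol 4.4.1 encourages.

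**The case against.** The strongest reply is that the gap is narrow. Sensitivity 3 removes post-medication data on the FAS with the primary model. Sensitivity 4, part 2, applies a same-arm hypothetical strategy; the RAS adds only the roughly 5% of patients whom the sample size section expects to be undosed or without a post-randomization rating, and the model differs by one interaction. The version log lists the retention of post-event data among changes made for FDA comments. All of this stands, and it supports leaving the primary data handling alone. It does not make the estimand text match: sensitivity 3 answers a placebo-based question, and sensitivity 4, part 2, changes several things at once.

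Four stronger readings are tempting but not supported.

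- *The SAP uses data that the protocol excludes.* Protocol 8.3.2 limits the primary analysis to "the MADRS total scores collected during the double-blind treatment period". The protocol uses that term for the 6-week phase, Table 1 places Visits 4 to 7 in it, and the SAP model uses only Days 7, 14, 28 and 42. A conflict arises only if the period ends at each patient's last dose, which the protocol does not say.
- *Sensitivity 2 is mislabelled.* It analyses every observed value regardless of events, so treatment policy is a defensible name; MAR is its missing-data assumption. The label that does not fit is the primary's.
- *The primary result is biased towards liafensine.* The direction depends on which arm uses more prohibited medication, and the documents do not say.
- *The trial's conclusion is likely to change.* The documents give no rates that would support this.

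**Conclusion.** The mismatch is certain from the text: a hypothetical target and label, with an estimator that follows treatment policy for observed post-event values. It is equally certain that no planned FAS analysis with the primary model estimates the stated quantity, and that no FAS or RAS analysis removes off-drug values when no prohibited medication was started.

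The size is not derivable. The single-source shifts of about 0.1 to 0.5 points (0.07 to 0.31 SE), and 0.95 points (0.59 SE) for the combined worst case, rest on assumed event rates and drug effects and can only illustrate. The combined case needs both extremes at once, and step 5 suggests that off-drug Day 42 values are few. The shift is probably small. This should be fixed as an alignment and labelling defect; it is not evidence that the primary test is invalid.

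**What to change.** Before unblinding, with the primary data handling unchanged:

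1. In SAP 5.4.1.1, state one strategy for each listed intercurrent event, chosen by event and not by whether data happen to be missing. To match SAP 5.4.1.2, this means treatment policy for prohibited medication and for treatment discontinuation, with MAR named as the missing-data assumption, and a separate explicit strategy for death. Remove the hypothetical label from the primary analysis and list the departure from Protocol 8.3.2 in SAP Table 4. The sensitivity 2 label can stay.
2. Add one supplementary FAS analysis with the primary model that estimates the protocol's hypothetical estimand: set MADRS values after the start of prohibited medication and after study-drug discontinuation to missing, then apply the same-arm MAR imputation.
3. Optionally, clarify that the double-blind treatment period in Protocol 8.3.2 means Visits 4 to 7, so that SAP 5.4.1.2 is plainly consistent with it.

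The cost is SAP wording and one extra analysis. The event information is already needed for sensitivities 3 and 4, and the primary test and its power do not change. The supplementary analysis is slightly less precise. If 5 to 10% of Day 42 values in each arm become missing with nothing recovered from earlier visits (89 vs 45, or 85 vs 42), its power for 4.5 points at 1-sided 0.05 is 86% or 84%, against 87% with complete data.

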5.4.1.3. Sensitivity Estimator

Four types of sensitivity analyses will be conducted on the primary endpoint.

1. A tipping point analysis to assess the robustness of the primary analysis results. The imputed missing values will be decreased or increased gradually, and treatment comparisons will be repeated. If the original result is significant and a large shift from the original imputed values needs to be done to reverse significance, the result is considered robust. The steps below will be followed.

If the primary analysis result is significant:

- 1) Increase each imputed value in the active arms by 1 and repeat the primary analysis using MMRM. If the treatment effect is still significant, each imputed value in the active arms will be further increased by 1 until the result is non-significant.
- 2) Repeat the tipping point analysis above but decrease each imputed value in the placebo arm by 1 until the result is non-significant.
- 3) Repeat the tipping point analysis by increasing each imputed value in the active arms by 1 and decreasing each imputed value in the placebo arm by 1 until the result is non-significant.

If the primary analysis result is non-significant:

- 1) Decrease each imputed value in the active arms by 1 and repeat the primary analysis using MMRM. If the treatment effect is still non-significant, each imputed value in the active arms will be further decreased by 1 until the result is significant.
- 2) Repeat the tipping point analysis above but increase each imputed value in the placebo arm by 1 until the result is significant.
- 3) Repeat the tipping point analysis by decreasing each imputed value in the active arms by 1 and increasing each imputed value in the placebo arm by 1 until the result is significant.

There are two active dose groups in this study. In the description above, significance or non-significance refers to the result after multiplicity adjustment, and shift from the imputed value only involves the active and placebo arms under tipping point analysis. The imputed values of the other active dose group will remain the same in the pooled analysis. A shift parameter will be applied to each dose arm separately in the pooled analysis. After each tipping point analyses is completed, up to 3 results before reaching

the tipping point, as well as the result that reverses statistical significance or non-significance will be reported.

2. MMRM without imputation

The same model in the primary analysis will be used without imputation using the treatment policy strategy per ICH E9(R1) (Polverejan 2023). This analysis will be used to assess the impact of imputing missing values based on the MAR assumption.

3. MMRM with imputation using pattern mixture model

This sensitivity estimator will be using a control-based multiple imputation method (Ratitch 2013). This sensitivity analysis does not rely on the MAR assumption. Data collected after initiation of prohibited medications will not be used unless otherwise specified. Missing data due to all ICEs will be handled per specifications below unless otherwise specified.

In this sensitivity analysis, imputation will be implemented using SAS MI procedure with FCS statement and REGPMM option, as well as MNAR statement with MODELOBS option to identify observations from the placebo arm for deriving the imputation models, ie, assuming all missing data will have a profile that equals the profile of the placebo arm for all time points. The variables to be used in the imputation are region, baseline values, and change from baseline values observed at Weeks 1, 2, 4, and 6.

One hundred fully imputed datasets will be created. The MMRM described in Section 5.4.1.2 will be used for treatment comparisons. Treatment effects (difference in LS means between treatment arms) from these 100 analyses will be combined to generate the final results using Rubin's method with SAS MIANALYZE procedure.

A tipping point analysis for this sensitivity analysis will also be conducted to assess the robustness of the result. The same steps described in the first sensitivity analysis will be followed.

4. Sensitivity Analyses based on RAS

A set of sensitivity analyses listed below will be performed using DGM4-positive patients in RAS. The same MMRM in the primary and sensitivity analyses described above will be carried out with the exclusion of the following fixed effect: treatment by baseline MADRS total score. In other words, the model will include the fixed effects of treatment, visit (categorical covariate), treatment by visit interaction, baseline MADRS total score (continuous covariate), and region.

The following analyses will be performed in this set of sensitivity analyses:

- 1) The primary analysis, as well as the 1st and 2nd sensitivity analyses based on FAS will be repeated using RAS.

- d) For subjects who used prohibited medications, data after initiation of prohibited medication will be imputed with non-missing data in the same arm while the subject is on study medication, same as b) above. If the subject terminates study medication early after initiation of prohibited medication, missing data after treatment termination will be imputed according to the cause of termination stated in Groups 1 to 3 above. See Appendix 8.6 for the implementation of multiple imputations.

5.4.2. Key Secondary Endpoint: Change in CGI-S from Baseline to Day 42, in DGM4-Positive Patients

The change in CGI-S from baseline (Visit 3, Day -1) to Day 42 (Visit 7) will be analyzed using the MMRM model without imputation similar to the one used in sensitivity analysis (2) for the primary efficacy endpoint described in Section 5.4.1.3. Separate figures with the mean change (\pm SD) and LS mean change (\pm SE) by visit will be displayed.

